8.7. Time-Based Analyses

Mean changes from baseline in the co-primary endpoints will be described in terms of time savings. The mean change from baseline at Week 52 in the active arm will be mapped back to the time point at which the mean change in the placebo arm was equal to the active arm change at Week 52. A cubic spline interpolation will be used for precise time mapping between visits. Similar mappings will be done for the mean changes \pm the SE of the mean changes. If a time mapping is outside the range spanned by the reference trajectory (e.g., mapping standard errors near the beginning or end of follow-up), time will be mapped off the range spanned by the reference trajectory via the line connecting the first visit for change from baseline (0, 0) for change from baseline measures and last visit measures. This time component test will be done based on all participants and for the mild and moderate subgroups.

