4.2. Introduction

Data processing, tabulation of descriptive statistics, calculation of inferential statistics, and graphical representations will use SAS (release 9.4 or higher). If the use of other software is required, the final clinical study report will specify the software that was used.

In general, summaries will be provided by study treatment group, unless otherwise noted. The column headings for the summaries will include the randomized treatment groups (Placebo BID, Simufilam 100 mg BID), unless otherwise noted.

Continuous (quantitative) variable summaries will include the number of participants with non-missing values (n), mean, 2-sided 95% confidence interval (CI), standard deviation (SD) and/or standard error (SE) if applicable, median, and minimum and maximum values.

Categorical (qualitative) variable summaries will include the frequency and percentage of participants who are in the category for each possible value. In general, the denominator for the percentage calculation will be based upon the total number of participants in the study population for the treatment groups (or cohorts) unless otherwise specified.

The minimum and maximum will be reported with the same degree of precision (i.e., the same number of decimal places) as the observed data. Measures of location (mean and median) and bounds of CIs will be reported to 1 degree of precision more than the observed data and measures of spread (SD and SE) will be reported to 2 degrees of precision more than the observed data. Percentages will be presented to 1 decimal place.

Statistical testing and inference methods for safety and efficacy analyses are described below. Efficacy results will be considered statistically significant after consideration of the strategy for controlling the Type 1 error as described in Section 6.1.2 of this SAP. Nominal p-values may be computed for other efficacy analyses as a measure of the association between the endpoint and the treatment effect rather than formal tests of hypotheses. Unless otherwise stated, all statistical tests will be conducted at the $\alpha = 0.05$ (two-sided) level, and a difference resulting in a p-value of ≤ 0.05 will be considered statistically significant. Corresponding 95% two-sided CIs will be presented for statistical tests.

All formal statistical comparisons will be based on LS means from the relevant contrasts in the mixed model for repeated measurements (MMRM) or analysis of covariance (ANCOVA).

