13.2. Efficacy Data

Table 6: Efficacy Data

Table Number	Population	Table Title/Summary
14.2.1	ITT	Summary of Primary, Secondary, and Exploratory Endpoints-Primary Efficacy model
14.2.2.1.1	ITT	Summary of Change from Baseline to Week 52 in ADAS-Cog12 Total Score by Visit and Treatment
14.2.2.1.2	ITT	Summary of Change from Baseline to Week 52 in ADAS-Cog12 Total Score By Visit and Treatment: Responder Analysis
14.2.2.1.3	ITT	Summary of Change from Baseline to Week 52 in ADAS-Cog12 Total Score By Visit and Treatment: Time Component Test
14.2.2.2	ITT-mild	Summary of Change from Baseline to Week 52 in ADAS-Cog12 Total Score By Visit and Treatment
14.2.2.3	ITT	Summary of Change from Baseline to Week 52 in ADAS-Cog12 Total Score By Visit and Treatment: Imputation Missing Not at Random
14.2.2.4.1	ITT	Summary of Change from Baseline to Week 52 in ADAS-Cog12 Total Score By Visit and Treatment Stratified by Mild (21-27)/Moderate (<21) AD Status
14.2.2.4.2	ITT	Summary of Change from Baseline to Week 52 in ADAS-Cog12 Total Score By Visit and Treatment Stratified by Mild (21-27)/Moderate (<21) AD Status: Responder Analysis
14.2.2.4.3	ITT	Summary of Change from Baseline to Week 52 in ADAS-Cog12 Total Score By Visit and Treatment Stratified by Mild (21-27)/Moderate (<21) AD Status: Time Component Test
14.2.2.5.1	ITT	Summary of Change from Baseline to Week 52 in ADAS-Cog12 Total Score By Visit and Treatment Stratified by Mild (20-27)/Moderate (<20) AD Status
14.2.2.5.2	ITT	Summary of Change from Baseline to Week 52 in ADAS-Cog12 Total Score By Visit and Treatment Stratified by Mild (20-27)/Moderate (<20) AD Status : Responder Analysis
14.2.2.6	ITT	Summary of Change from Baseline to Week 52 in ADAS-Cog12 Total Score By Visit and Treatment Stratified by Age
14.2.2.7	ITT	Summary of Change from Baseline to Week 52 in ADAS-Cog12 Total Score By Visit and Treatment Stratified by Gender
14.2.2.8	ITT	Summary of Change from Baseline to Week 52 in ADAS-Cog12 Total Score By Visit and Treatment Stratified by Ethnicity
14.2.2.9	ITT	Summary of Change from Baseline to Week 52 in ADAS-Cog12 Total Score By Visit and Treatment Stratified by Race

Table Number	Population	Table Title/Summary
14.2.2.10	ITT	Summary of Change from Baseline to Week 52 in ADAS-Cog12 Total Score By Visit and Treatment Stratified by ApoE Genotype
14.2.2.11	ITT	Summary of Change from Baseline to Week 52 in ADAS-Cog12 Total Score By Visit and Treatment Stratified by Baseline Cognitive Enhancer Status

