14.2.3.1.1	ITT	Summary of Change from Baseline to Week 52 in ADCS-ADL Total Score By Visit and Treatment
14.2.3.1.2	ITT	Summary of Change from Baseline to Week 52 in ADCS-ADL Total Score By Visit and Treatment: Responder Analysis
14.2.3.1.3	ITT	Summary of Change from Baseline to Week 52 in ADCS-ADL Total Score By Visit and Treatment: Time Component Test
14.2.3.2	ITT-mild	Summary of Change from Baseline to Week 52 in ADCS-ADL Total Score By Visit and Treatment
14.2.3.3	ITT	Summary of Change from Baseline to Week 52 in ADCS-ADL Total Score By Visit and Treatment: Imputation Missing Not at Random
14.2.3.4.1	ITT	Summary of Change from Baseline to Week 52 in ADCS-ADL Total Score By Visit and Treatment Stratified by Mild (21-27)/Moderate (<21) AD Status
14.2.3.4.2	ITT	Summary of Change from Baseline to Week 52 in ADCS-ADL Total Score By Visit and Treatment Stratified by Mild (21-27)/Moderate (<21) AD Status : Responder Analysis
14.2.3.4.3	ITT	Summary of Change from Baseline to Week 52 in ADCS-ADL Total Score By Visit and Treatment Stratified by Mild (21-27)/Moderate (<21) AD Status : Time Component Test
14.2.3.5.1	ITT	Summary of Change from Baseline to Week 52 in ADCS-ADL Total Score By Visit and Treatment Stratified by Mild (20-27)/Moderate (<20) AD Status
14.2.3.5.2	ITT	Summary of Change from Baseline to Week 52 in ADCS-ADL Total Score By Visit and Treatment Stratified by Mild (20-27)/Moderate (<20) AD Status : Responder Analysis
14.2.3.6	ITT	Summary of Change from Baseline to Week 52 in ADCS-ADL Total Score By Visit and Treatment Stratified by Age
14.2.3.7	ITT	Summary of Change from Baseline to Week 52 in ADCS-ADL Total Score By Visit and Treatment Stratified by Gender
14.2.3.8	ITT	Summary of Change from Baseline to Week 52 in ADCS-ADL Total Score By Visit and Treatment Stratified by Ethnicity
14.2.3.9	ITT	Summary of Change from Baseline to Week 52 in ADCS-ADL Total Score By Visit and Treatment Stratified by Race
14.2.3.10	ITT	Summary of Change from Baseline to Week 52 in ADCS-ADL Total Score By Visit and Treatment Stratified by ApoE Genotype
14.2.3.11	ITT	Summary of Change from Baseline to Week 52 in ADCS-ADL Total Score By Visit and Treatment Stratified by Baseline Cognitive Enhancer Status
14.2.4.1	ITT	Summary of Change from Baseline to Week 52 in iADRS Total Score By Visit and Treatment
14.2.4.2	ITT-mild	Summary of Change from Baseline to Week 52 in iADRS Total Score By Visit and Treatment

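### The SAP 8.7 error bar for time saved leaves out the placebo curve's sampling error: on the natural reading it is too narrow by about 1.2 to 1.4 times, and no interval or test is defined

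*SAP*

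**What the plan says.** SAP 8.7 defines the analysis: "The mean change from baseline at Week 52 in the active arm will be mapped back to the time point" where the placebo curve takes that same value. Between visits, "A cubic spline interpolation will be used for precise time mapping between visits". For uncertainty it says only that "Similar mappings will be done for the mean changes" plus and minus the SE of those changes, and it names no arm. Values that fall off the placebo curve are placed on a straight line through the origin and the last visit.

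On scope and label: "This time component test will be done based on all participants and for the mild and moderate subgroups". In SAP 13.2 the main tables carry the same label, for example "Summary of Change from Baseline to Week 52 in ADAS-Cog12 Total Score By Visit and Treatment: Time Component Test" (14.2.2.1.3) and "Summary of Change from Baseline to Week 52 in ADCS-ADL Total Score By Visit and Treatment: Time Component Test" (14.2.3.1.3). There are mild/moderate versions, and matching figures in 13.5.

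Two other places bear on the reading. SAP 4.2 promises: "Corresponding 95% two-sided CIs will be presented for statistical tests". SAP 1 (Overview), describing the inferential tables, lists within-group mean changes separately from the between-group difference. The time analysis is not in the testing hierarchy of SAP 6.1.3.

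**The concern.** Time saved is 52 weeks minus the week at which the placebo curve equals the active Week 52 mean. Both the active mean and the placebo curve are estimates. In 8.7 a mean change belongs to an arm, and the placebo curve is the reference, so the SE is most naturally that of the active Week 52 mean. The mapped bar then reflects the active arm's error alone, and no other section adds the placebo arm's.

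The bar sits on the time axis beside the estimate of delay, so a reader is likely to take it as the precision of that delay. It would look better than the data support, for both co-primaries and both severity subgroups. The word *test* adds to the problem because 8.7 gives no statistic, p-value or interval, whereas SAP 8.5 and 8.6 name the CMH test.

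**Working it through.** **Inputs from the documents.** SAP 2.2: placebo change 5.0 points, SD 8.5, 45% effect (2.25 points), 300 per arm, 90% power, two-sided 0.05, 20% dropout, 804 randomised. SAP 2.3: about 77 sites. SAP 2.4: 1:1 allocation. These are ADAS-Cog values; the documents give none for ADCS-ADL.

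**Assumed.** Shape of the placebo decline, SD of change at intermediate visits, correlation between visits, and correlation between the arms' LS means.

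**1. The plan's own figure.** n per arm = 2 × (1.960 + 1.282)² × 8.5² / 2.25² ≈ 300, and 300 / 0.8 = 375. Both reproduce. The SAP states no figure for the precision of time saved.

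**2. The bar as written.** The active-arm SE is 8.5 / √300 = 0.491 points. With linear decline the placebo slope is 5.0 / 52 = 0.0962 points per week. The bar is 0.491 / 0.0962 = 5.1 weeks each side.

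**3. What it should carry.** Let a be the active Week 52 mean, f the placebo curve and t* the week at which f equals a. By the delta method

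Var(t*) ≈ [V_a + V_p(t*) − 2·Cov] / f′(t*)².

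The mapped bar keeps V_a only. With equal arms, s = (SD at t*) / 8.5 and correlation r between the arm means,

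correct SE / mapped SE = √(1 + s² − 2rs).

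| Case | SD at t* | r | Ratio |
|---|---|---|---|
| No effect, t* = 52 | 8.5 | 0 | √2 = 1.41 |
| 45% slowing, t* = 0.55 × 52 = 28.6 | 8.5 | 0 | 1.41 |
| 45% slowing | 6.5 | 0 | √(1 + 0.585) = 1.26 |
| No effect | 8.5 | 0.10 to 0.17 | √1.80 to √1.66 = 1.34 to 1.29 |
| 45% slowing | 8.5 | 0.15 | √1.70 = 1.30 |
| 45% slowing | 6.5 | 0.15 | √(1.585 − 0.229) = 1.16 |

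With independent arms at 45% slowing, the omitted share of the variance is 0.585 / 1.585 = 37% up to 50%. A correlation can arise from shared pooled-site terms. With about 77 sites, the pooling rule of SAP 6.1.6 and an assumed site-size CV of 0.5 to 1.0, it came out at 0.10 to 0.17; equal site sizes give 0. With equal arms the ratio does not depend on n, so the larger final sample does not remove the problem.

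**4. Coverage of the one-SE bar.** In closed form, P(|Z| < 1/1.41) = 52% and P(|Z| < 1/1.26) = 57%, against 68%. Simulation inverted the spline with the SAP's off-range line: 300 or 322 per arm (402 × 0.8 ≈ 322), linear or mildly accelerating decline, visit SDs rising from 4.5 or 6.0 to 8.5, AR(1) 0.6, effects of 0, 25 and 45%, 2,500 trials per scenario.

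| Setting | Spread of mapped time / mapped half-width | Coverage |
|---|---|---|
| Independent arms | 1.33 to 1.50 | 51 to 58% |
| Correlation 0.15 | 1.27 to 1.41 | 54 to 59% |
| SD flat at 8.5, independent | 1.42 to 1.60 | 49 to 55% |

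A separate simulation (300 and 150 per arm, Week 28 SD 6.2 to 8.5, adjacent-visit correlation 0.7 or 0.9) gave ratios of 1.26 to 1.49 and coverage of about 51 to 58%.

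**5. A bar that just clears zero.** The treatment difference then equals one active-arm SE. Against the SE of the difference, √2 times larger, z = 1/√2 = 0.71 and p = 0.48; a correct one-SE bar would correspond to p = 0.32. With no true effect, the mapped bar lies wholly on the favourable side in 21 to 26% of simulated trials, against 16% for a correct bar.

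**The case against.** The strongest objection is that 8.7 does not fix the SE. If the SE of the treatment difference is meant (√2 × 0.491 = 0.694 points), the bar is about 7.0 to 7.4 weeks and covers about 68 to 75%, which is about right or slightly wide. That is true, and the finding is conditional on the active-arm reading. But Section 8.7 attaches mean changes to arms, and SAP 1 keeps them apart from between-group differences, so the difference reading is the less natural one. Leaving the choice open until the data are unblinded is itself a fault.

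Second, the display is descriptive. The mapped values are never called a confidence interval, and valid inference for the same Week 52 contrast comes from the MMRM. This stands as a limit on importance. It does not make the bar a correct statement of precision, and it sits poorly with the label *test*.

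Third, the exact factor depends on SDs and correlations that the documents do not give, and simulated ratios run above the delta-method range. This also stands. Every scenario tried puts the bar on the narrow side; only the amount varies.

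Fourth, comparing a 95% interval with a one-SE bar mixes confidence levels. This is fair, and the cost is put on a like-for-like basis under the fix.

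**Conclusion.** The concern holds. On the natural reading, the only error bar planned for time saved omits the placebo curve's sampling error and is too narrow by about 1.2 to 1.4 times by the delta method, and by up to 1.6 in the most unfavourable simulated scenarios. The low end needs a placebo SD at the mapped week well below 8.5, or a positive correlation between the arm means; the value 1.41 applies near no effect with independent arms. Under any reading, 8.7 leaves the SE unnamed and uses the word *test* without defining one. The consequence is limited to a supplementary display: no decision rule uses it and the co-primary tests are untouched. It should still be corrected, because it is planned for both co-primaries and both severity subgroups, and SAP 1 says planned analyses may go into study reports, submissions and manuscripts.

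**What to change.** In SAP 8.7, replace the plus/minus SE mapping with a 95% confidence interval for time saved that carries both arms' error, and fix one method before unblinding:

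- **Bootstrap.** Resample participants within arm and MMSE stratum, refit the model, re-map in each replicate, and take percentile limits. State how site pooling under 6.1.6 is handled across replicates.
- **Delta method.** Use the covariance matrix of the MMRM LS means for both arms, including the cross-covariance. This is cheaper.

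In simulation at 322 per arm with linear decline, nominal 95% intervals covered 93 to 96% (bootstrap) and 90 to 95% (delta method). The bootstrap check drew from the visit-mean covariance and did not resample participants. Neither method was checked at subgroup size, so a short check there is advisable before choosing.

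Apply the method to both co-primaries and to the mild and moderate subgroups. If the mean plus/minus SE mapping is kept as a display, name the arm and state that it is not a confidence interval for time saved. Remove *test* from 8.7 and from the table and figure titles unless a valid test is defined.

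The cost is SAP wording, some programming and, for the bootstrap, run time; no new data. The intervals will be wider: a simulated 95% half-width of about 11 to 14 weeks, against about 8 to 10 weeks if the mapped one-SE bars of 4 to 5 weeks were multiplied by 1.96.

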8.8. Pooling With Other Studies

Pending the outcomes of individual studies, data from Protocol PTI-125-07 may be pooled with data from Protocol PTI-125-06. These pooled analyses will include data from weeks 0 – 52 from Protocol PTI-125-06 to match the duration of Protocol PTI-125-07. Objectives and estimands for the pooled data will mirror those in Protocol PTI-125-07. Analyses will also be similar but will include an additional categorical fixed effect of study.

9. Safety and Tolerability Analysis

All safety analyses will be performed on the safety analysis set.

Safety measures including AEs, clinical laboratory values, physical examination findings, neurologic examination findings, vital signs, ECGs, and concomitant medication usage will be summarized descriptively. No inferential statistical tests will be performed, unless otherwise specified. For quantitative variables, descriptive statistics including number of observations, mean, median, standard deviation, minimum, and maximum will be presented for observed and change from baseline values at each study visit. Qualitative variables will be summarized using counts and percentages.

For all safety and tolerability analyses, participants will be analyzed by the actual treatment and dose received and, if applicable, overall.

All safety and tolerability data will be presented in participant listings.

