2.2. Sample Size and Power

Planned enrollment was approximately seven hundred fifty (750) participants with mild-to-moderate AD dementia. The sample size was determined by a power analysis of ADAS-Cog using data from a similar population over 52 weeks. This analysis determined that group sizes of 300 are powered to show a 45% mean difference from placebo at 52 weeks with 90% power and a two-sided significance level of 0.05. The power calculation assumes a true mean change from baseline for placebo of 5.0 points and a standard deviation of 8.5 points. Assuming a drop-out of 20%, each treatment group should enroll approximately 375 participants. The final sample size was 804 randomized participants.

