This study is considered a registration study. Statistical tests will be regarded as formal tests of specific hypotheses.

The data from nominal/scheduled protocol clinic visits will be included in visit-based summary tables. Unscheduled assessments, if they occur, and the ET visit data will be mapped to scheduled assessments according to the visit windows defined in section 6.1.5 for all safety and efficacy analyses. See Section 6.1.4 and 6.1.5 of this SAP for more details.

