6.1.3. Multiple Comparisons

The co-primary endpoints of ADAS-Cog12, and ADCS-ADL will each be tested at $p=0.05$ using the ITT analysis set. Multiplicity among secondary endpoints in the ITT analysis set will be controlled using a hierarchical, gatekeeping strategy. Secondary endpoints will be tested in the following order: iADRS, CDR-SB, ZBI, MMSE, and NPI-10. Testing will proceed in this order

until the first non-significant p value ($p > 0.05$). The first endpoint with $p > 0.05$ and all subsequent endpoints in the order will be declared non-significant, and all endpoints preceding the first non-significant test will be declared significant.

For the set of significant endpoints in the ITT analysis set, the corresponding endpoints in the mild subgroup (ITT-mild analysis set) will be tested. Testing for the mild cohort will proceed in the same order as for the secondary endpoints referenced above until the first non-significant p value. The first endpoint with $p > 0.05$ and all subsequent endpoints in the order will be declared non-significant, and all endpoints preceding the first non-significant test will be declared significant.

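### SAP 8.8 lets the decision to pool with PTI-125-06 follow the study results, so any pooled estimate and p-value would be selected on the data that enter them

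*SAP*

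**What the plan says.** SAP 8.8 is one short paragraph. It opens with "Pending the outcomes of individual studies, data from Protocol PTI-125-07 may be pooled with data from Protocol PTI-125-06". It limits PTI-125-06 to Weeks 0-52 and adds "Objectives and estimands for the pooled data will mirror those in Protocol PTI-125-07" and "Analyses will also be similar but will include an additional categorical fixed effect of study". It does not state which outcomes count, in which direction, on which endpoint, who decides, or when. It does not call the pooled analysis supportive, exploratory or post hoc.

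The testing strategy in SAP 6.1.3 covers this study only. For the co-primaries, "The co-primary endpoints of ADAS-Cog12, and ADCS-ADL will each be tested at $p=0.05$ using the ITT analysis set"; for the secondaries, "Secondary endpoints will be tested in the following order: iADRS, CDR-SB, ZBI, MMSE, and NPI-10", followed by the mild subgroup. The pooled analysis has no place in that sequence. On endpoints outside the strategy, SAP 4.2 says "Nominal p-values may be computed for other efficacy analyses as a measure of the association between the endpoint and the treatment effect", and distinguishes these from formal tests. A few lines later, after describing this study as a registration study, the same section says "Statistical tests will be regarded as formal tests of specific hypotheses".

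Protocol 11.3 describes no pooling. Protocol 11.3.1 defines study success as significance on both co-primary comparisons.

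**The concern.** The individual results are functions of the same data that form the pooled estimate. If those results decide whether a pooled analysis is produced, the pooled analyses that appear are a selected set. Their estimates are biased, and their p-values do not have the stated error rate given that they are shown. Reading the opening word of 8.8 as mere timing does not remove this, because the permissive verb leaves the choice open once results are known.

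Reporting makes it matter more. SAP section 1 presents the document as an a priori plan and promises a special label only for post hoc or unplanned analyses. Because 8.8 is in the SAP, a pooled result that was chosen after the fact could be reported as pre-specified, with this trial's own objectives and estimands attached. A reader would have no means of knowing what had been selected on.

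**Working it through.** **The plan's own figure.** Inputs from SAP 2.2: difference 45% of 5.0 = 2.25 points, SD 8.5, two-sided alpha 0.05, power 90%.

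n per group = 2(1.960 + 1.282)² × 8.5² / 2.25² = 300 after rounding up; 300/0.80 = 375. Both stated figures reproduce. The SAP gives no figure for the pooled analysis.

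**Standard errors.** One study with 300 per group: 8.5 × √(2/300) = 0.694 points. Pooled at equal information: 0.694/√2 = 0.491 points.

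**Set-up.** No effect in either study; one endpoint; independent statistics z₁ (PTI-125-07) and z₂ (PTI-125-06), each N(0,1), positive values favouring simufilam. With a fixed study effect, the pooled statistic at equal information is (z₁ + z₂)/√2. Favourable significance means z > 1.96, which has probability 2.5%. Equal information is an assumption, because the documents do not give the size of PTI-125-06. Information ratios from 0.5 to 2 were also run. Since the SAP states no trigger, the triggers below are illustrations. Results are from 4 million simulated pairs; the bias is mean pooled z × 0.491.

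| Pooling done only if | Chance trigger is met | Favourable significant pooled result, given pooling | Mean pooled z | Bias (points) |
|---|---|---|---|---|
| Always | 100% | 2.5% | 0 | 0 |
| Neither study favourably significant | 95.1% | 0.9% | -0.085 | -0.04 |
| PTI-125-07 misses, both lean favourable | 23.7% | 6.8% | 1.071 | 0.53 |
| Both lean favourable | 25.0% | 9.7% | 1.128 | 0.55 |
| At least one with favourable p < 0.20 | 19.0% | 13.1% | 1.176 | 0.58 |
| At least one favourably significant | 4.9% | 33% | 1.633 | 0.80 |

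**Checks by hand.**
- Both lean favourable: each z is then half-normal with mean √(2/π) = 0.798, so mean pooled z = 2 × 0.798/√2 = 1.128.
- At least one favourably significant: probability 1 - 0.975² = 4.9%. Mean pooled z = (2 × 0.0584 × 0.975/√2)/0.0494 = 1.63, where 0.0584 is the normal density at 1.96.
- The first and last conditional triggers are complementary: 0.951 × 0.0091 + 0.0495 × 0.3285 = 0.0087 + 0.0163 = 0.025. Selection moves the error between the two cases and does not raise the total. The chance of pooling and finding a favourable significant pooled result can never exceed 2.5%.

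**Sensitivity to the size of PTI-125-06.** Over ratios 0.5 to 2, the conditional error stays at about 0.9% (neither significant), 9.5% to 9.7% (both lean favourable) and 33% to 34% (at least one significant). The bias under the last trigger is 0.91 points at ratio 0.5 and 0.64 at ratio 2, because the pooled SE goes from 0.567 to 0.401.

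**The case against.** The strongest reply is that nothing confirmatory rests on 8.8. Success is defined in Protocol 11.3.1 and SAP 6.1.3 on this study's own co-primaries, and no text lets a pooled result rescue a miss. SAP 4.2 ties significance to the error-control strategy and treats efficacy p-values outside it as nominal. The sentence on formal tests follows a statement about this study, not about a pool of two. Section 13 lists no pooled table or figure. PTI-125-06 has its own plan, which may fix the pooling rule and is not available here. All of this stands.

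It disposes of a stronger reading that a reader might infer: that 8.8 adds a second formal test and inflates the trial's type I error. One can calculate that, under no effect and at equal information, either this study or the pooled test reaches two-sided 0.05 with probability 8.3% (4.2% against 2.5% in the favourable direction). That figure presupposes a rule under which either result counts as a win, and the documents contain no such rule.

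It is also fair that the 33% belongs to a trigger met only 4.9% of the time under no effect, that another plausible trigger takes the error below nominal, and that requiring both co-primaries would lower the absolute rates.

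What does not fall is the selection itself. A nominal p-value shown only when results invite it is still selected, and the estimate is biased whatever label it carries.

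**Conclusion.** The point holds as a matter of selective production and labelling. As written, 8.8 would yield a pooled estimate and p-value chosen on their own data. The distortion cannot be given one size or even one sign: with no effect, one endpoint and equal information, the conditional favourable-direction error runs from about 0.9% to about 33%, against 2.5% for unconditional pooling. The upper end carries a bias of about 0.8 points, 0.80/2.25 = 36% of the planned difference. These are scenarios, since the SAP writes no trigger. The co-primary test of PTI-125-07 and its alpha are untouched, and the pooled p-value is best read as nominal under SAP 4.2, which 8.8 should say. This is a cheap improvement, not a flaw in the primary analysis.

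**What to change.** Rewrite SAP 8.8 along these lines: Weeks 0-52 data from PTI-125-06 and PTI-125-07 will be pooled regardless of the outcome of either study. The pooled analysis is supportive; estimates, 95% confidence intervals and nominal p-values will be reported, and no claim of significance will be made from it. The estimate from each study will be shown beside the pooled estimate.

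With pooling fixed in advance, the favourable-direction error returns to 2.5%, the selection bias is zero, and the precision is kept (SE about 0.49 points against 0.69 for one study, at equal information). A pre-written pooling rule would be second best: it makes the selection known and calculable but does not remove it. A treatment-by-study term would help to show discordant studies, but it is secondary, since the side-by-side estimates already do much of that.

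The cost is SAP wording and the sponsor's option to decide on pooling after seeing the results.
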